5.4 Data Analysis (and sample size)

This is a parallel, randomized control study. The researcher analyzing results will be blinded to the patient's group. A statistician will be hired to analyze data and a statistician from C2E2 (UBC) has reviewed the study design. Normally distributed data will be analyzed using repeated measures analysis of variance (ANOVA) to calculate changes over time (baseline, six-months, one-year) within each group. Between groups analyses on differences from baseline will be analyzed using independent *t*-tests. Statistical significance will be set *a priori* as *p*<.05. Continuous variables will be described by group using mean (SD) (or median (P25, P75) if the data are skewed); and categorical variables will be described by frequency (percent).

To calculate effect size for the intervention group, we considered the moderate effect sizes reported in exercise studies measuring cardiorespiratory changes (e.g., Huang et al. (2016) (40) reported a moderately high effect size of 0.64 for aerobic changes following an exercise program in older adults). Using G-power software (*alpha* = .05), the

sample size required to achieve 80% power to detect an effect is 22 per group (two-tailed, or repeated measures design) (44). Based on the data from Malmo and colleagues (26) reporting a large effect size (1.0) for the difference in time spent in AF pre- and post-exercise, a sample size of less than 10 participants would achieve a power of 80%. The AF studies to-date report low attrition rates. For example, Pathak et al. (19) reported 10% attrition in the risk factor intervention group, and Malmo et al.(26) reported a 0% attrition in the three-month interval-training program. Given that the Richmond Cardiac Rehabilitation program similarly reports low drop-out rates (of approximately 2%), we have allowed for greater than 10% attrition. Including 40 participants in the intervention arm, and 40 participants in the control arm will allow for more than 10% drop out while still maintaining adequate power to detect an effect.

6. Summary and Impacts on Practice

Richmond has experience in recruiting patients with AF, cardiac rehabilitation, and bariatric diet therapy program. Our Richmond team of specialists, combined with strong partnerships with our colleagues at VGH that have experience with research trials will help guide us in implementing a successful research project.

This study uses a reproducible intensive supervised cardiac rehabilitation program that includes exercise, diet, and risk factor modification for patients with paroxysmal, non-valvular AF. We expect that a six-month intervention will show significant improvement in fitness and weight loss and improvements in AF symptoms and frequency, and cardiovascular risk factors when compared to a control group with paroxysmal AF and similar baseline characteristics who do not receive a supervised diet and exercise program. The supervised program is followed by a six-month home-based exercise and diet program, which gives us the opportunity to look further at adherence, and whether the benefits of the six-month intensive hospital-based program can be sustained at home. A follow-up study could retest the baseline results at two years and up to five years if effects are sustained. If both the phase 1 cardiac rehabilitation and diet six-month program and phase 2 home-based program are successful, then this study could be repeated with only a home-based or community-based intervention as a lower cost alternative.

The missing piece in studies of antiarrhythmic therapy and catheter ablation for patients with paroxysmal AF is the inclusion of risk factor modification. With attention to diet, exercise, and cardiovascular risk factor modification it should be possible to obtain high rates of maintenance of normal sinus rhythm. This exercise, diet and risk factor modification model can be added to usual care or catheter ablation aiming for optimal five-year reduction in AF. Alternatively patients could be randomized to diet and exercise, versus usual care post-catheter ablation. In future trials, a loop recorder could possibly be implanted to give more accurate information of AF recurrence rates.

Future studies with longer follow up can also focus on a more robust cost benefit analysis. Demonstrating that an exercise and diet intervention is cost-effective and efficacious in reducing the burden of AF can potentially be used to encourage government funding and physicians to prescribe exercise and diet to all patients with paroxysmal AF. Ultimately a large, multi-centre trial that combines exercise, diet, and risk factor modification in patients with paroxysmal AF compared to usual care can be designed to determine whether this intervention reduces mortality, cardiac events, and stroke.

Dissemination plans:

We plan to submit an abstract summarizing the mid-point study results in hope of an oral presentation at the Canadian Cardiovascular Congress October 2019. We then plan to write a research paper and publish our results (regardless of the direction of our findings) in the Canadian Cardiovascular Society Journal (the Canadian Journal of Cardiology).

[name] presented the background and research plan at Internal Medicine rounds Richmond Hospital in November, 2017 and will present the background research and study proposal and methods at Grand Rounds Richmond Hospital in June 2018. Once the results are completed [name] will present again at Internal Medicine Rounds Richmond Hospital. [name] and or [name] will have the opportunity to present the results at VGH Cardiology rounds.

If we observe significant improvements in AF risk factors, we plan to apply for funding through the Heart and Stroke Foundation's "Grants-in-aid" program to support operating costs of a larger scale (longer duration) study on exercise, diet, and lifestyle intervention in patients with AF

The final study results will be reported after completion of one-year follow up.

References

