AF is a symptom of underlying cardiovascular risk factors and a marker of increased mortality and morbidity. We need to shift our focus to the treatment of these underlying risk factors in patients with AF. Diet, exercise, and risk factor management can be used to modify these risk factors both in the short term, and potentially with sustained effect. This study employs a randomized design to test a six-month supervised intensive exercise, diet, and risk factor management program, followed by a six-month home-based exercise and diet program. Based on previous studies, we hypothesize that this should lead to an improvement in cardiovascular risk factors, a reduction in AF burden, and possible improvements in left atrial remodeling.

3. Hypotheses:

- i) Patients with paroxysmal non-valvular AF that complete a supervised six-month program of exercise, diet, and life style modification will exhibit reduced recurrent AF and reduced cardiovascular risk factors when compared to a similar group of patients who receive usual care.
- ii) The intervention group will show improvements in physical fitness, cardiovascular risk factors, and AF symptoms and severity at both the six-month and one-year follow-up assessments compared to the usual care group.
- iii) A reduction in medication costs and emergency room visits will help offset the cost of the intervention.

4. Objectives: The objectives of this study are to demonstrate changes in symptoms and severity of AF following an exercise, diet, and risk factor modification intervention in patients with AF. Demonstrating that a comprehensive cardiac rehabilitation program is feasible and cost-effective will help us design a future larger-scale, multi-centre study.

i) Primary outcomes include:

- a. Burden of AF, including both frequency and symptoms.
 - i. The frequency of AF will be measured with 48-hour Holter monitor recording, looking at percent of time in AF at baseline, six months and one year follow up.

- ii. Symptoms of AF will be assessed using the Canadian Cardiovascular Society Severity in Atrial Fibrillation Scale (CCS-SAF) (31), and the Atrial Fibrillation Symptom Severity Scale (AFSS) (32); both are validated tools to assess burden of AF symptoms.
- iii. The 36-item Short Form Survey Instrument (33) and the EQ-5D-3L (34) will be used to measure quality of life.

ii) Secondary outcomes include:

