5.4 Data Collection

All measurements (save demographics and medical history) will be collected at baseline, six months, and one year in both groups.

1. Patient demographics: age, sex, ethnicity, education, income, and living situation.
2. Medical history: medications and cost; hospital emergency visit and admission < 1yr, known coronary artery disease defined by prior myocardial infarction or presence of 50% stenosis on CT or invasive angiogram; admission for heart failure, prior stroke; average daily glasses of alcohol, smoking status (including frequency and amount); the Canadian Cardiovascular Society Severity in Atrial Fibrillation (CCS-SAF) Scale, (31) the Atrial Fibrillation Symptom Severity Scale (AFSS) (32), the 36-item Short Form Survey Instrument (33) and the EQ-5D-3L (34).
3. Anthropometrics: Body mass index (BMI), waist circumference, neck circumference, modified mallampati score (41) and blood pressure.
4. Blood work: Hemoglobin AIC, total cholesterol, creatinine, low-density lipoprotein, high-density lipoprotein, triglycerides, ALT, c-reactive protein, electrolytes, and brain natriuretic peptide.
5. Level 3 home sleep study: Apnea-hypopnea index, minimum saturation, and time spent with saturation < 90%, Epworth Sleepiness Scale (42).
6. Godin's leisure time physical activity measure will be used measure baseline physical activity levels (43).
7. Exercise Stress Test at maximal effort: Maximum METs achieved, peak heart rate, and rating of perceived exertion.
8. 48-hour Holter monitor: 48-hour heart rhythm monitor to determine frequency and duration of AF measured as the percent of time in AF.
9. Echocardiography at base line and one year: measurements: LA volume, LA pressure, diastolic function, grade, calculated biplane LVEF, and left ventricular hypertrophy.

All data sheets are attached in section 9 of the application. There is a data sheet for each: sleep study, echo, blood work, stress test, physical exam, and Holter monitor.

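### The between-arm t-test on change ignores baseline and no test is named for skewed or ordinal primary outcomes, so power is lost that baseline adjustment would recover

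*Combined protocol and SAP*

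**What the plan says.** Section 5.4 Data Analysis (and sample size) names two tests. Within each group, "Normally distributed data will be analyzed using repeated measures analysis of variance (ANOVA) to calculate changes over time". Between arms, "Between groups analyses on differences from baseline will be analyzed using independent *t*-tests". No baseline covariate appears in either.

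The same section foresees skew, but only when describing data: "Continuous variables will be described by group using mean (SD) (or median (P25, P75) if the data are skewed". For categorical data it says that "categorical variables will be described by frequency (percent" and names no test.

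The primary outcomes are in section 4, item i. For AF frequency, "The frequency of AF will be measured with 48-hour Holter monitor recording, looking at percent of time in AF". Symptoms are scored on the CCS-SAF and the AFSS. Section 5.2 enrols paroxysmal AF. Section 5.4 Data Collection has the Holter and the symptom scales measured at baseline, six months and one year, so the baseline values will be available.

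**The concern.** Percent time in AF is bounded between 0 and 100. In paroxysmal AF, some two-day recordings can be expected to show none and others a great deal. CCS-SAF is a graded scale. Neither can be expected to be normal, so the plan's two tests either are applied to data they do not suit or leave these outcomes with no planned test.

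A separate weakness affects every continuous outcome. A t-test on change subtracts the whole baseline value, however weakly it predicts follow-up, and so carries baseline noise into the comparison. ANCOVA subtracts only the part that predicts.

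At stake is whether 40 per arm can show a useful effect on a primary outcome, and whether the method for that outcome is fixed before its distribution is seen.

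**Working it through.** **1. The plan's own figure.** The plan states 22 per group for effect size 0.64, 80% power, alpha 0.05, two-tailed. A paired t-test gives n = 21.2, so 22; the figure reproduces as a within-group calculation. For the planned between-arm t-test, d = 0.64 gives 39.3, so 40 per arm. Power is 80.7% at 40 and 76.4% at 36 (40 less 10% dropout). There is little slack to absorb an inefficient test.

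**2. Baseline adjustment with normal data.** Let σ be the SD at each visit and ρ the baseline-to-follow-up correlation.

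- Variance of change: 2σ²(1 − ρ)
- Residual variance under ANCOVA: σ²(1 − ρ²)
- Ratio, ANCOVA to change: (1 + ρ)/2, which is 0.65, 0.75 and 0.85 at ρ = 0.3, 0.5 and 0.7

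For a shift of 0.64σ and 40 per arm, approximate power is Φ(δ√(40/2) − 1.96), with δ = 0.64/√(2(1 − ρ)) for change and 0.64/√(1 − ρ²) for ANCOVA.

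| ρ | δ, change | Power, change | δ, ANCOVA | Power, ANCOVA |
|---|---|---|---|---|
| 0.3 | 0.541 | 68% | 0.671 | 85% |
| 0.5 | 0.640 | 82% | 0.739 | 91% |
| 0.7 | 0.826 | 96% | 0.896 | 98% |

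Simulation (6,000 trials per cell) agrees: 66, 81 and 95% against 84, 91 and 97%.

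**3. Holter percent, first model.** All inputs except the 40 per arm are assumptions. Zero readings 40–70%; non-zero values Beta(0.5, 1); Gaussian copula with correlation 0.3–0.5; effect of 20 points more zero readings and 40% less burden in the rest; 1,500–3,000 trials per cell.

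| Effect | t-test on change | Raw ANCOVA | Rank ANCOVA |
|---|---|---|---|
| Occurrence and amount | 27–47% | 54–73% | 56–71% |
| Amount only | 7–24% | 13–36% | 5–12% |
| Occurrence only | 13–22% | 20–38% | 38–70% |

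Type I error was about 4–6% for each method.

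**4. Holter percent, second model.** Capped log-normal positive values (median 5%, log-SD 1.5), 30–70% zeros, correlation 0.3–0.7, 4,000 trials per cell, 40 per arm. With an effect on both occurrence and amount: t-test on change 18–44%, raw ANCOVA 34–67%, rank ANCOVA 51–92%. Null rejection was 4.2–5.2% for the t-test and 4.7–5.6% for rank ANCOVA. At 36 per arm, 50% zeros and correlation 0.5, power was 26.3%, 48.2% and 66.1%. Baseline adjustment therefore supplies (48.2 − 26.3)/(66.1 − 26.3) = 21.9/39.8 = 55% of the gain, and ranking the rest. With an amount-only effect and 50% zeros, rank ANCOVA (11–19%) again falls below the t-test on change (16–32%).

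**5. CCS-SAF.** The documents do not give the number of levels; five are assumed, with a latent shift of 0.64 SD and 40 per arm. At correlations 0.3, 0.5 and 0.7:

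- t-test on change: 59, 71, 88%
- raw ANCOVA: 79, 85, 94%
- rank ANCOVA: 78, 84, 93%

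Here nearly all the loss comes from not adjusting for baseline.

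**The case against.** Four points can be made for the plan.

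**The text may not commit to a t-test on skewed data.** The analysis description opens with normally distributed data, and the t-test sentence can be read under that condition. This stands as a reading. It leaves the primary Holter comparison with no named test, which is still a gap. The plan says that a statistician will be hired and that another has reviewed the design. That softens the gap but does not fill it.

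**The inputs are invented.** The documents give no share of zero Holters, SD or correlation. Raising the correlation to 0.7–0.8 in the first model lifts the t-test on change to 42–75%. The only effect on time in AF in the plan is 1.0; if it applied to between-arm change, power would be about 99% at 36–40 per arm. But the plan describes that figure as a pre-post difference, so it need not carry over to a comparison of arms. The objection rules out an unconditional claim that the trial has little chance of success.

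**Mean percent time is a legitimate target.** This stands. Raw ANCOVA keeps that target and recovers much of the lost power.

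**Ranks are not always better.** This also stands. A reader might infer that non-normality is the whole problem and rank analysis the cure. The calculations do not support that: unranked ANCOVA does about as well as rank ANCOVA in the first model's combined-effect case, and ranks fall below the planned test when treatment only shortens AF.

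**Conclusion.** The concern holds as a loss of power and a gap in specification. The plan's between-arm comparison is less efficient than one using baseline values it already collects, and no inferential test is named for skewed or ordinal outcomes.

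Under the first model with a combined effect, the planned test has about 27–47% power against about 54–73% for ANCOVA on raw or ranked values. Baseline adjustment supplies most of that gain, though only about half in the second model. For normal outcomes the loss is 17 points at correlation 0.3 and 2 points at 0.7 (table in step 2). The direction of the baseline-adjustment gain was the same in every setting examined. Its size for Holter percent and CCS-SAF depends on inputs absent from the documents.

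A reader might infer that the planned t-test would give false-positive results on such data. The null simulations do not show this. Whether ranks help depends on how treatment acts. The hypothesis of reduced recurrent AF leans towards an effect on occurrence, but the documents do not settle it.

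**What to change.** In section 5.4 Data Analysis:

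- **Continuous outcomes:** replace the t-test on change with ANCOVA of the follow-up value on arm and baseline value.
- **Percent time in AF:** name in advance one baseline-adjusted primary analysis: raw ANCOVA with robust or permutation inference, rank ANCOVA, or a two-part model. Report the share of each arm with no AF on Holter beside it. If rank ANCOVA is chosen, report medians too, because its effect is not a difference in mean percent time.
- **CCS-SAF:** use a proportional-odds model with baseline class as covariate.

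The cost is a few sentences of SAP text and slightly more analysis; no new data are needed. The real trade-off is the Holter choice. Rank ANCOVA gains power if treatment makes more patients AF-free, and loses it, even against the t-test on change, if treatment only shortens AF in those who still have it. The choice should therefore follow from the expected mechanism and be fixed before unblinded data are seen.

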2. Check ins from research assistant by phone if participant's exhibit a significant reduction in physical activity detected by the step tracker. Participants will be informed that data from their step trackers will be downloaded regularly to monitor daily steps and intensity of activity (based on HR). No other data can be monitored through the step tracker. If a participant's activity drops 50% below the previous month's average over a two-week period, the research assistant will telephone the participant to ensure equipment is working properly, to discuss barriers, and to encourage them to maintain the fitness regime.
3. An optional weekly walking group will be available for participants (leaving Minoru park) to encourage adherence.

Treatment of Obstructive Sleep Apnea (OSA): This will involve the same treatment offered to the control arm (see section 5.3, above).

A six-month exercise program that begins with low-intensity exercise, followed by a three-month supervised interval training should be sufficient to effect changes in modifiable risk factors including BMI, blood pressure, and glycemic control. It should also be sufficient to lead to increased exercise capacity. A meta-analysis on cardiofit exercise programs in older adults reported an average of 23 weeks in length resulted in significant improvements in cardiorespiratory fitness (40). Months six to twelve will test the efficacy of a home-based program and investigate whether the results at six months are sustained at one year.

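### The only analysis using all three visits is run within each arm, nothing makes the planned between-arm t-tests decisive, and no test addresses whether an arm difference at six months persists at one year.

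*Combined protocol and SAP*

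**What the plan says.** Section 5.4 Data Analysis (and sample size) names two analyses for normally distributed outcomes. The first is "repeated measures analysis of variance (ANOVA) to calculate changes over time (baseline, six-months, one-year) within each group". The second follows at once: "Between groups analyses on differences from baseline will be analyzed using independent" t-tests. One significance level, p<.05, covers both. The section does not tie the t-tests to a visit, names no arm-by-visit test, and does not say which analysis decides whether the program worked.

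Elsewhere the protocol frames its question in two ways. The hypotheses in section 3 are comparative; hypothesis ii asks for improvement against usual care at six months and at one year. The objective in section 4 is "to demonstrate changes in symptoms and severity of AF following an exercise, diet, and risk factor modification intervention", with no comparator in that sentence. The closing paragraph of section 5.3.2 says months six to twelve will "investigate whether the results at six months are sustained at one year", and section 6 returns to whether the hospital-based benefit holds at home. Neither place names a test or a criterion for this.

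**The concern.** A p-value for change over time inside one arm reflects everything that moved that arm, not only the program. Several influences act on both arms here. All participants receive usual AF care, and sleep apnea treatment is offered equally. Controls also get a step tracker and an activity handout (5.3.1). AF is described in the Rationale as a disease of exacerbations and remissions, so some drift after enrolment is plausible in either arm.

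The sample-size paragraph also leans towards the within-arm view. It cites a study that "reported a moderately high effect size of 0.64 for aerobic changes following an exercise program in older adults" and another "reporting a large effect size (1.0) for the difference in time spent in AF pre- and post-exercise, a sample size of less than 10 participants". As shown below, its figure of 22 per group matches a one-group paired test.

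Two things are at stake. A significant within-arm ANOVA could be quoted beside, or in place of, the randomised comparison, although the protocol itself criticises earlier AF studies for lack of randomisation. And the question about months six to twelve has no planned between-arm answer: t-tests on change from baseline, taken visit by visit, do not test whether the arm difference altered between the two visits.

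**Working it through.** **Inputs from the documents (5.1 and 5.4 Data Analysis).** 40 randomised per arm; two-sided alpha 0.05; power 80%; effect sizes 0.64 (fitness) and 1.0 (time in AF, pre-post); dropout allowance of more than 10%. Taking 10% dropout, 40 × (1 − 0.10) = 36 completers per arm.

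**Assumptions, not in the documents.** Normal outcomes with SD 1, equal correlation ρ = 0.5 to 0.7 between visits, and a shared shift s = 0.2 to 0.4 SD at both follow-up visits in both arms, with no program effect.

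**Step 1: the plan's own figure.** For a one-group paired t-test the noncentrality is d√n. With d = 0.64 and n = 22 it is 0.64 × √22 = 3.00, which gives 81.7% power; 22 is the smallest n reaching 80%. So the stated 22 reproduces as a within-group test. For the planned between-arm t-test the noncentrality is d√(n/2), with d read in SDs of the change score. At d = 0.64 this needs 40 per arm (80.7% power); power is 76.4% at 36 per arm and 54.5% at 22.

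**Step 2: the within-arm ANOVA when both arms improve equally.** With visit means (0, s, s), the sum of squared deviations from their average is (2/3)s². The noncentrality is λ = n(2/3)s²/(1 − ρ), on 2 and 70 degrees of freedom at n = 36.

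| ρ | s | λ | Program-arm ANOVA significant |
|---|---|---|---|
| 0.5 | 0.2 | 36 × 0.667 × 0.04/0.5 = 1.92 | 21% |
| 0.5 | 0.3 | 36 × 0.667 × 0.09/0.5 = 4.32 | 43% |
| 0.5 | 0.4 | 36 × 0.667 × 0.16/0.5 = 7.68 | 68% |
| 0.7 | 0.2 | 36 × 0.667 × 0.04/0.3 = 3.20 | 33% |
| 0.7 | 0.3 | 36 × 0.667 × 0.09/0.3 = 7.20 | 65% |
| 0.7 | 0.4 | 36 × 0.667 × 0.16/0.3 = 12.8 | 89% |

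Simulation with 10,000 runs at ρ = 0.5 agrees: 22%, 42% and 68%.

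**Step 3: the planned between-arm t-test in the same trials.** The shared shift cancels. At ρ = 0.5 the simulated two-sided rejection rate was 4.8% to 5.1% at each visit. An arm-by-visit test was also near 5%. Counting a success at either of two visits gave about 9%, which is one reason to name the visit.

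**Step 4: persistence from six months to one year.** A paired test of the six-to-twelve-month change within one arm (n = 36) has 80% power for 0.48 SD of that change, and 46% for 0.32 SD (half of 0.64). It therefore misses a loss of 0.32 SD 54% of the time. The between-arm version, the change in the arm difference, has noncentrality d√(36/2). It reaches 80% power only at about 0.67 SD of the change and has 27% power at 0.32. In outcome units, the SD of the change is √(2(1 − ρ)): 1.00 at ρ = 0.5 and 0.77 at ρ = 0.7. So 0.67 corresponds to 0.67 and 0.52 outcome SD respectively.

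**The case against.** The strongest reply is that the randomised comparison is already in the plan. The sentence after the ANOVA provides t-tests between arms on change from baseline, shared improvement cancels in them, and the hypotheses are explicitly against usual care at both follow-ups. This stands. A reader might infer that the trial will judge efficacy on within-arm p-values, or on significance in the program arm but not in control. The documents state no such rule.

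It is also fair that the 20-90% range is simply the ANOVA's power to detect a real change that was assumed, and that the shifts and correlations come from outside the documents. The plan limits the ANOVA to normally distributed data, and it does not say whether percent time in AF will qualify. Recruitment at routine follow-up visits weakens the case for strong regression to the mean.

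On persistence, a reader might infer that 'sustained' will be declared from a non-significant within-arm change. No such criterion is written, and a t-test on one-year change would already estimate the one-year arm difference. What remains unanswered is that no visit is named for the t-tests, neither analysis is made subordinate to the other, and no planned test or stated criterion covers the course of the arm difference after six months.

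**Conclusion.** The point holds in a limited form. The between-arm t-tests are valid and keep about 5% error per visit. The weakness is that the only three-visit analysis is within-arm, carries equal standing at p<.05, and cannot distinguish a program effect from common improvement. Under the assumed shared shifts of 0.2 to 0.4 SD with correlation 0.5 to 0.7 and 36 per arm, it is significant in about 20-90% of trials with no program effect. That range shows what the within-arm p-value cannot support; it is not a false-positive rate for the trial's planned comparison. Separately, the question of whether benefit persists to one year is asked twice and has no between-arm test or stated criterion. The omissions can be read directly from the text; the size depends on the assumptions above.

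**What to change.** Replace the two within-arm ANOVAs with one repeated-measures mixed model on all randomised participants: visit, arm-by-visit, baseline as a covariate (or a common baseline mean for the arms), and within-participant correlation. Use it for outcomes where a normal model is reasonable. Report the arm difference at six months and at one year with 95% CIs, and state that efficacy conclusions rest on these. Judge 'sustained' on the one-year arm difference and its CI, with the change in the arm difference between visits as a supporting estimate. Give within-arm changes as means with CIs and no p-values. Reword the section 4 objective as a difference from usual care.

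This needs no extra participants or visits; it changes analysis wording and one model specification. The downsides are fewer p-values to quote and an imprecise change-in-difference contrast (80% power at 36 per arm only for about 0.67 SD of the six-to-twelve-month change), so that contrast should not be the criterion for persistence.

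### The plan asks whether six-month results are sustained at one year, but plans no estimate of how the between-arm effect changes between those visits

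*Combined protocol and SAP*

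**What the plan says.** The question appears three times in the narrative. The section on the current state of knowledge lists persistence after supervision ends as unknown. The closing paragraph of 5.3.2 says that the second six months will "investigate whether the results at six months are sustained at one year". Section 6 says that the home phase will show "whether the benefits of the six-month intensive hospital-based program can be sustained at home".

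The one formal hypothesis about one year is hypothesis ii in section 3. It expects improvement in the intervention group "at both the six-month and one-year follow-up assessments compared to the usual care group". It compares the arms at each visit and does not compare the visits with each other.

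Section 5.4 Data Analysis (and sample size) plans two analyses for normally distributed data:

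- within each arm, a "repeated measures analysis of variance (ANOVA) to calculate changes over time (baseline, six-months, one-year) within each group";
- between arms, "Between groups analyses on differences from baseline will be analyzed using independent *t*-tests", with no visit named.

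The threshold is p<.05 throughout. The section names no contrast of one year with six months, no group-by-visit interaction and no definition of *sustained*.

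**The concern.** Whether a benefit is sustained is a question about the between-arm effect at one year relative to the effect at six months. No planned analysis estimates that quantity. The only planned analysis that takes in both follow-up visits at once is the within-arm ANOVA. Its null hypothesis is that all three visit means are equal, so it responds to a benefit that came and went just as it does to one that came and stayed. The t-tests each look back to baseline, and two separate verdicts do not add up to a measure of how much was kept.

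The stake is how the one-year result will be worded. Section 6 makes a possible follow-up at two to five years depend on effects being sustained. It makes a possible home-based or community-based repeat depend on both phases being successful. With no estimate specified, *sustained* or *lost* could be attached to the result on grounds that do not bear on it.

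**Working it through.** **Inputs from section 5.4 Data Analysis.** Effect size 0.64 (aerobic fitness); two-sided alpha .05; 40 randomised per arm; 10% attrition leaves 40 × 0.9 = 36 per arm.

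**Assumptions.** 0.64 is in SDs of change and also serves as the six-month between-arm effect; normal data; equal variances and equal correlations between visits; no change in the control arm. The share of the effect kept at one year is varied.

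**1. The plan's own figure.** It states that the "sample size required to achieve 80% power to detect an effect is 22 per group (two-tailed, or repeated measures design". A paired t-test with d = 0.64 and n = 22 has noncentrality 0.64 × √22 = 3.00 on 21 df and power 81.7%, so 22 is reproduced. An independent two-sample test would need 40 per arm. The match with a paired test supports reading 0.64 in SDs of change.

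**2. The three-visit ANOVA in the intervention arm.** With the SD of change set to 1, the error variance is 0.5, and the noncentrality is λ = n × Σ(μ − mean)² / 0.5, on 2 and 2(n − 1) df.

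| Visit means (baseline, 6 m, 1 y) | Σ(μ − mean)² | λ at n = 36 | Power, n = 36 | Power, n = 40 |
|---|---|---|---|---|
| Fully lost (0, 0.64, 0) | 0.273 | 19.7 | 98.0% | 98.9% |
| Half kept (0, 0.64, 0.32) | 0.205 | 14.7 | 93.0% | 95.4% |
| Fully kept (0, 0.64, 0.64) | 0.273 | 19.7 | 98.0% | 98.9% |

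Full loss and full retention have the same sum of squares, so the F test cannot tell them apart. If 0.64 is instead in raw SDs, with visit correlation 0.3 to 0.8, power at n = 40 runs from 94.4% to above 99.9% and is again the same for both patterns.

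**3. The one-year t-test between arms.** The noncentrality is δ / √(2/n). At n = 36, √(2/36) = 0.236.

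| Effect kept at one year | δ | Significant, n = 36 | Significant, n = 40 |
|---|---|---|---|
| None | 0 | 5.0% | 5.0% |
| Half | 0.32 | 26.8% | 29.3% |
| All | 0.64 | 76.4% | 80.7% |

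This test does respond to loss. After complete loss it is significant only at the error rate.

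**4. Reading the two t-tests side by side** (10,000 simulated trials per scenario, 36 per arm).

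| Effect kept | Significant at 6 m | Significant at both | Significant at 6 m only |
|---|---|---|---|
| None | 76.5% | 3.3% | 73.3% |
| Half | 75.9% | 25.0% | 51.0% |
| All | 75.7% | 62.9% | 12.9% |

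With everything kept, 12.85 / 75.71 = 17% of trials significant at six months are non-significant at one year (11.51 / 80.79 = 14% at 40 per arm). With half lost, a quarter of all trials are significant at both visits.

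**5. Precision of the missing contrast.** Under the same assumptions, the one-year minus six-month between-arm difference has standard error √(2/n) in SDs of change. The 95% half-width is 1.994 × 0.236 = 0.47 at 36 per arm and 1.991 × 0.224 = 0.45 at 40. That is 0.47 / 0.64 = 73% and 0.45 / 0.64 = 70% of the effect. As a significance test, the contrast would detect loss of half the effect in 26.8% (36 per arm) or 29.3% (40 per arm) of trials, so a non-significant result would not show retention.

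**The case against.** The strongest reply is that the between-arm t-tests already answer the one-year question in the form the plan formally poses it. Hypothesis ii asks for improvement over usual care at each follow-up, and retention relative to six months is not among the numbered hypotheses, objectives or outcomes. This stands. A reader might infer that the planned tests miss the one-year question altogether, or that the trial is set to call a vanished benefit sustained. The documents support neither. After complete loss the one-year test is significant in 5% of trials, and both visits are significant in about 3%.

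It is also fair to say that section 5.4 gives the ANOVA no role in showing sustainment; it is there to describe change over time. The 98% therefore shows what the ANOVA cannot tell us. It is not a forecast of false claims.

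The 17% partly reflects power of about 76% at 36 per arm, which is a matter of sample size. That does not rescue the comparison of two p-values: it is one reason why the comparison does not measure retention.

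Finally, a formal retention margin would be out of reach. Excluding loss of half the effect (0.32, for illustration) would succeed in only about 27% of fully retained trials at 36 per arm, and 80% power would need about 2 × (1.96 + 0.84)² / 0.32² ≈ 154 per arm. In a trial of 80 patients meant to inform a larger one, that argues for an estimate with an interval and no pass/fail rule.

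What remains is that the narrative poses the retention question three times and the analysis section offers nothing that measures the answer.

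**Conclusion.** The point holds as a gap in the analysis plan. Presence of benefit at one year can be tested as planned, once the visits are named. Change in benefit from six months to one year is not estimated anywhere. At the plan's effect size the ANOVA is about equally likely to be significant (about 98% at 36 per arm) after full loss and after full retention. A pair of t-test results misleads in both directions: about 17% apparent loss under full retention among trials significant at six months, and about 25% significant at both visits when half is lost.

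These figures rest on the assumptions listed above. In particular, 0.64 is a fitness effect, and no figure is offered here for percent time in AF or the symptom scales. That the ANOVA has equal power for the two patterns does not depend on the effect size, given equal variances and correlations across visits.

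The gap does not undermine hypothesis ii. It affects what may be said about whether the six-month results last.

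**What to change.** In 5.4 Data Analysis (and sample size):

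- State that the between-arm t-tests on change from baseline are done at six months and at one year.
- For each outcome measured at both follow-up visits, add the one-year minus six-month between-arm difference with a 95% CI, for example from one model with group, visit and their interaction. Echocardiography is excluded because it is done only at baseline and one year.
- State that neither the ANOVA p-value, nor a non-significant comparison of six months with one year, nor the pattern of two p-values will be read as showing that benefit was sustained or lost.
- Report the contrast as an estimate, without a pass/fail margin. Word the one-year t-test as showing, or not showing, a benefit over usual care at that visit.

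The cost is a few sentences and one contrast on data already to be collected, with no extra visits or patients. The drawback is the wide interval: the trial will usually have to report that retention is uncertain.
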